Appendix 3: Satiety Questionnaire.....	24

Study Synopsis

STUDY TITLE:	Comparison of postprandial glycemic and insulinemic response to a Cookie with or without added Fibersym after three days of pre-feeding: An acute, double-blind, randomized controlled clinical trial
STUDY NUMBER/ VERSION DATE:	GIL-1852; version: June 31, 2018
INVESTIGATORS:	GI Labs: [name], PhD; [name]
SPONSOR:	MGP Ingredients, Inc, Contact: [name], VP Ingredients R&D and Chief Science Officer
STUDY SITE:	Glycemic Index Laboratories, Inc. (GI Labs)
STUDY OBJECTIVE(S):	Primary Objective: to compare the postprandial glucose incremental area under the curve (IAUC) after the Fibersym containing carbohydrate load with the glucose IAUC after the control meal
INTERVENTION PRODUCT	Fibersym® is a resistant modified wheat starch in which over 85% of the total starch is resistant starch as measured by AOAC method 991.43. Fibersym can easily be added to food formulations as it provides a smooth texture, neutral flavour and white color.
STUDY POPULATION	Healthy adult males or females (n=15), aged 18-75 years with BMI between 18.5 and 35 kg/m ² . Each subject will have to fulfill all inclusion criteria and will not be allowed to meet any of the exclusion criteria.
TEST MEALS:	
 1. Control Cookie 2. Cookie with added Fibersym 
The difference in the cookies is the presence of the Fibersym, meals will therefore be matched for available carbohydrate.

STUDY DESIGN AND RATIONALE	
Design: acute, double blind, randomized, controlled clinical trial. Subjects will come in fasting and be given either the Control or Fibersym containing cookie. Postprandial glucose and insulin levels will be measured over 2 hours.
 
As Fibersym is recommended to be consumed on a daily basis, for 3 days prior to each test meal visit, subjects will be given cookies to be consumed 3 times daily for 3 days, ie control cookies will be consumed for 3 days before the control cookie test meal and Fibersym cookies

	
before the Fibersym cookie test meal. Each subject will be provided with enough cookies to consume 1 cookie with each meal (breakfast, lunch and dinner) over the 3 days. The Fibersym containing cookie will deliver about 29g/day of dietary fibre.

PROTOCOL SUMMARY	
Participants will be recruited by GI labs from their existing subject pool through email and/or advertising posters and leaflets. Volunteers will have the study explained to them prior to providing informed consent.
 
Visit 1: Screening: A pre-study examination will verify that subjects qualify for study inclusion. A number of parameters will be assessed: including blood pressure; weight, height, BMI, and brief medical history.
 
Visit 2-3: Eligible subjects will be randomized using an online randomization calculator. Eligible subjects will be studied on 2 separate days over a period of 4 weeks or less. Prior to each test meal they will be provided with enough cookies to consume 3 times/day over 3 days and instructed to start consuming these 3 days before their visit. They will also be provided with a calorie appropriate, standard dinner to be consumed on the evening before their test meal. The interval between successive tests will be no less than 6 days and no more than 4 weeks.
 
On each test day, participants will come to GI Labs in the morning after a 10-12h overnight fast (except for water). Participants will be asked to maintain stable dietary and activity habits throughout their participation and refrain from drinking alcohol and from unusual levels of food intake or physical activity for 24h before each test. Before the start of the test meal, subjects will be asked whether they consumed the provided cookies over the last 3 days as instructed and the standard dinner the evening before. Subjects will be asked to complete a 3d dietary food record and symptom diary before each test visit. If any subject is not feeling well or has not complied with the preceding experimental conditions, the test will not be carried out and will be rescheduled for another day. On each test day, two fasting fingerprick blood samples will be collected at -5min and 0min. Questionnaires to record satiety and GI symptoms will be administered. Participants will then be given the test food together with 250ml of water and instructed to consume this over 15minutes. Additional blood samples will be collected 15, 30, 46, 60, 90 and 120min after the start of the test meal. Satiety Questionnaires will be administered at the same time intervals. GI symptom questionnaires

	will be filled out at 2h in addition to fasting.
CRITERIA FOR EVALUATION:	
EFFICACY: Primary outcome is comparison of the glucose IAUC of the Fibersym meal with the control meal.
 
Secondary outcomes: comparison of the insulin (IAUC) of the Fibersym meal with the control meal, comparison of glucose and insulin levels at each time point and satiety scores at each time point.
 
SAFETY: Adverse events.

STATISTICAL METHODS:	Results for all foods in a series will be compared by GLM ANOVA. After demonstrating significant heterogeneity, the significance of the differences will be tested using Tukey method to adjust for multiple comparisons
Ethics Board Approval	The investigator will be responsible for submission of the study to the Western Institutional Research Board. Prior to submission of the application, the sponsors and all co-investigators will be given the opportunity to review the application. Submission of the application will only take place if all parties agree. The Western Institutional Review Board® meets all requirements of the US Food and Drug Administration (FDA), the Department of Health and Human Services (DHHS), the Canadian Health Protection Branch (HPB), Canadian Institutes of Health Research (CIHR) and the European Community Guidelines. Participants will not be enrolled into the study until they have had the study procedures explained to them, had a chance to ask questions, and given their voluntary consent by signing the consent form. Participants who do not understand English will not be enrolled.
Subject Selection Criteria	
Inclusion criteria:
 
 1. Male or non-pregnant females, 18-75 years of age, inclusive 2. Body mass index (BMI) between 18.5 and 35 kg/m² inclusive at screening. 3. Systolic blood pressure < 130mmHg, Diastolic Blood pressure <90mmHg. 4. Willing to maintain habitual diet, physical activity pattern, and body weight throughout the trial. 5. Subject is willing to abstain from strenuous exercise, or consume alcoholic drinks 24hours before study days. 6. Absence of health conditions that would prevent fulfillment of study requirements as judged by the Investigator on the basis

of medical history.

7. Understanding the study procedures and willing to provide informed consent to participate in the study and authorization to release relevant protected health information to the study investigator.
8. Female subjects are willing to use a contraceptive method to avoid pregnancy during the study period.

Exclusion criteria:

1. Failure to meet any one of the inclusion criteria
2. Smokers
3. Known history of diabetes, gastrointestinal, liver, kidney, or cardiovascular (including, but not limited to, atherosclerotic disease, history of myocardial infarction, peripheral arterial disease, stroke), and pulmonary disease
4. Use of medications known to influence carbohydrate metabolism, including, but not limited to adrenergic blockers, diuretics, thiazolidinediones, metformin and systemic corticosteroids within 4 weeks of the screening visit, or with any condition which might, in the opinion of [name] either: 1) make participation dangerous to the subject or to others, or 2) affect the results.
5. Use of antibiotics within 4 weeks of start of study
6. Major trauma or surgical event within 3 months of screening.
7. Unwillingness or inability to comply with the experimental procedures and to follow GI Labs safety guidelines.
8. Known intolerance, sensitivity or allergy to any ingredients in the study products.
9. Extreme dietary habits, as judged by the Investigator (i.e. Atkins diet, very high protein diets, etc).
10. Change in body weight of >3.5kg within 4 weeks of the screening visit.
11. History of cancer in the prior two years, except for non-melanoma skin cancer.
12. Exposure to any non-registered drug product within 30 d prior to screening.
13. Pregnancy or breastfeeding
14. Any history of an eating disorder (e.g., anorexia nervosa, bulimia nervosa, binge eating) diagnosed by a health professional

1. Background and Rationale

Consumption of whole grains have been recommended by most health agencies to increase dietary fibre intake with the ultimate goal to help maintain a healthy body weight and improve insulin sensitivity. Despite these recommendations, most individuals do not meet the recommended 25–35 g per day. Therefore, innovative ideas to increase dietary fibre intake are needed. One approach is to incorporate either by substituting the carbohydrate in a food or by adding isolated fibers to products. MGP Ingredients had developed several resistant starches including, Fibersym® RW, a resistant starch 4 (RS4), which are easily incorporated into foods and would help increase the dietary fiber content of food products, however, RS4 is not included among the eight dietary fibre sources recently approved by FDA.

The FDA defines dietary fiber as "non-digestible soluble and insoluble carbohydrates (with 3 or more monomeric units), and lignin that are intrinsic and intact in plants; isolated or synthetic non-digestible carbohydrates (with 3 or more monomeric units) determined by FDA to have physiological effects that are beneficial to human health." The list of currently approved fibers under the new FDA food labeling regulations that has a compliance date of January 1, 2020 includes RS2 but not RS4. Clinical research studies have demonstrated a broad range of health benefits after consumption of RS including attenuation of postprandial blood glucose and insulin levels, improving the profile of the microbiota, reduction in colon cancer and increased fat oxidation and mineral absorption (Higgins et al, 2004; Jenkins et al, 1998, 2000; Robertson et al, 2005; So et al, 2007, Topping et all, 2003). Several different forms of RS have been developed, these include RS1 which is composed of starch granules embedded in indigestible plant material, RS2 is native granular starch with a B-type x-ray pattern, RS3 is crystallized starch and maltodextrins made by alternate cooking/cooling processes on starchy materials and finally, RS4 is chemically modified starch typically through esterification, crosslinking or transglycosylation.

The majority of the studies demonstrating a reduction in postprandial glucose and insulin levels kept the total carbohydrate of the meals the same, ie they achieved the attenuation of the glucose by substituting the available carbohydrate with the resistant starch (Haub et al, 2010) but not all (Al-Tamimi et al, 2010). The last trial suggests that RS4xl may differ from the other RS in that it may be inherently physiologically active itself, not unlike the viscous fibres.

Fibersym® is a resistant modified wheat starch in which over 85% of the total starch is resistant starch as measured by AOAC method 991.43. Fibersym can easily be added to food formulations as it provides a smooth texture, neutral flavour and white color. It is meant to be consumed on a regular basis and doses up to 40g/day can be tolerated. The effect of the Fibersym containing products on postprandial glucose and insulin levels when compared to a control meal containing the same amount of available carbohydrate is not known. This study therefore investigates the effect of the acute effect of control or Fibersym cookie matched for available carbohydrate after 3 day habituation.

2. Study Objectives

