2.2 Secondary objectives

- To compare the 2hour postprandial insulin incremental area under the curve (IAUC) after the Fibersym containing carbohydrate load with the control meal
- To compare the individual postprandial glucose and insulin responses at each time point after the Fibersym containing carbohydrate load with the control meal
- To compare the GI symptoms after the three days of pre-feeding of Fibersym cookies with the control meal
- To compare the satiety scores after the Fibersym containing carbohydrate load with the control meal
- SAFETY: GI symptoms and Adverse events.

3. Subject Selection

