4.3 Test Foods

There will be two test foods:

1. Control Cookie
2. Cookie with added Fibersym

The difference in the cookies is the presence of the Fibersym, meals will therefore be matched for available carbohydrate. Both test meals will be consumed with 250ml of water.

During the 3-day pre-feeding period, subject will consume 9 cookies per day with the aim to provide approximately 29g of fibre per day from the Fibersym cookies. For the test breakfasts, the subject will consume approximately 3 cookies containing 50g available carbohydrate. The Fibersym cookies will

deliver approximately 10g of fibre. Once the cookies are baked they will be sent out for macronutrient analysis and the final weight of the cookies fed will be adjusted accordingly.

Table 1: Approximate composition of the test meals*

	Approx. # cookies	Weight (g)	Protein (g)	Fat (g)	Total carbohydrate (g)	Dietary Fibre (g)	Available carbohydrate (g)
Control Cookie	3	90	3.4	10.5	50.2	0.2	50
Fibersym cookie	3	100	3.4	10.5	60.2	10.2	50

* Once the cookies are baked they will be sent out for macronutrient analysis and the final weight of the cookies fed will be adjusted accordingly.

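### The synopsis supplies one cookie per meal in pre-feeding, which gives about 10 g of fibre a day instead of the stated 29 g; the count that fits is three per meal, as in Section 4.3

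*Combined protocol and SAP*

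**What the plan says.** Two places in the combined protocol and SAP give a number of cookies for the 3-day pre-feeding period.

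- **Study Synopsis, Study Design and Rationale:** "Each subject will be provided with enough cookies to consume 1 cookie with each meal (breakfast, lunch and dinner) over the 3 days". The sentence after it reads: "The Fibersym containing cookie will deliver about 29g/day of dietary fibre".
- **Section 4.3, Test Foods:** "subject will consume 9 cookies per day with the aim to provide approximately 29g of fibre per day".

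Section 4.3 also fixes the fibre content per cookie. On the test meal it says: "For the test breakfasts, the subject will consume approximately 3 cookies containing 50g available carbohydrate". It then says that the Fibersym cookies will "deliver approximately 10g of fibre". Table 1 lists 3 Fibersym cookies at 100 g in weight and 10.2 g of dietary fibre.

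The protocol summary and Section 4.1 say only that cookies are eaten three times a day for 3 days, with no number per occasion. The flow chart in Section 4.2 gives no count. Section 6.2 says that each subject will be told the serving size but does not state it. Nothing says which section governs if they differ.

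**The concern.** The synopsis and Section 4.3 name the same daily fibre dose but differ threefold in the number of cookies that supplies it. Both cannot be right with one cookie composition.

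Pre-feeding is a defining feature of this design: it is in the study title, and the rationale frames the question as the response after habituation. If product were dispensed by the synopsis line, subjects would habituate on about one third of the stated dose. The secondary objective "To compare the GI symptoms after the three days of pre-feeding of Fibersym cookies with the control meal" would then describe tolerability at about 10 g/day, while the report would give about 29 g/day.

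An under-supply of this kind could go unnoticed. Asking subjects whether they ate what they were given would not reveal it, because they would have complied.

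**Working it through.** **Inputs**

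- Fibre in 3 Fibersym cookies: 10 g (Section 4.3 text) or 10.2 g (Table 1).
- Weight of 3 Fibersym cookies: 100 g (Table 1).
- Stated pre-feeding dose: 29 g/day (synopsis and Section 4.3).
- Counts: 1 × 3 meals = 3 cookies/day (synopsis); 9 cookies/day (Section 4.3).

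**Fibre per cookie**

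10 / 3 = 3.33 g; 10.2 / 3 = 3.40 g.

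**Can the stated 29 g/day be reproduced?** Daily fibre = cookies per day × fibre per cookie.

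| Count | Fibre per day | Share of 29 g | Cookies over 3 days | Fibre over 3 days |
|---|---|---|---|---|
| Synopsis, 3/day | 10.0–10.2 g | 34.5–35.2% | 9 | 30.0–30.6 g |
| Section 4.3, 9/day | 30.0–30.6 g | 103.4–105.5% | 27 | 90.0–91.8 g |
| Implied by 29 g/day | 29 g | 100% | – | 29 × 3 = 87 g |

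The synopsis count does not reproduce the figure. The Section 4.3 count does, within the approximation that the text allows. Reaching 29 g exactly would take 29 / 3.40 = 8.5 to 29 / 3.33 = 8.7 cookies, so 9 is the nearest whole number.

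**Per meal**

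29 / 3 = 9.67 g of fibre is needed at each meal. In cookies, that is 9.67 / 3.40 = 2.84 to 9.67 / 3.33 = 2.90, so 3. One cookie carries 3.33 to 3.40 g.

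**Size of the shortfall at 3/day**

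29 − 10.2 = 18.8 g to 29 − 10.0 = 19.0 g per day; over 3 days, 56.4 to 57.0 g.

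**Could the adjustment after baking close the gap?**

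Section 4.3 says "the final weight of the cookies fed will be adjusted accordingly" once the macronutrient analysis is in. For one cookie to carry 9.67 g of fibre at the Table 1 composition it would have to weigh (100 / 3) × 2.84 = 94.8 g to (100 / 3) × 2.90 = 96.7 g. Table 1 implies 33.3 g per cookie and 100 g for the whole 3-cookie portion. A correction for analysed composition does not stretch to a threefold change.

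**The case against.** The strongest reply is that this is loose wording in a summary and that the detailed section is already right. The synopsis uses the singular for a whole test meal elsewhere: "Subjects will come in fasting and be given either the Control or Fibersym containing cookie", although Section 4.3 defines that meal as about 3 cookies. If one cookie means one portion, then one portion per meal gives about 30 g/day and the sections agree in substance. This reading is credible and may well be what was meant. It does not rescue the line as written, because the synopsis gives a numeral in a supply instruction and Table 1 counts cookies individually. Under this reading too, the clear wording is three cookies per meal.

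A second reply is that 1 cookie × 3 meals × 3 days is also 9 cookies, or about 30 g over the whole period, so the dose might be a 3-day total mislabelled as daily. This cannot be fully excluded. It would require the same mislabelling of the dose in both sections, and also of the 9-cookie count in Section 4.3. The background describes up to 40 g/day as tolerated, so about 30 g/day is plausible on the document's own terms.

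A third reply is that other records would catch an under-supply: the 3-day food record in the protocol summary, the 3-day supplement record in Section 4.1, the compliance checks in the flow chart, and the intake logs in Section 6.1. They might. No section says that any of them captures a count, and the contents of the logs are not in the documents.

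It also stands that the harm is conditional. Nothing says that dispensing follows the synopsis, and no sample size or analysis depends on the count.

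**Conclusion.** The concern holds. The synopsis count of 3 cookies a day delivers 10.0 to 10.2 g of fibre, about 35% of the 29 g/day stated beside it. The 9 cookies a day in Section 4.3 deliver 30.0 to 30.6 g and are consistent with that dose. The synopsis line is the one to correct.

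This rests on the approximate composition in Section 4.3 and Table 1, and on reading the 29 g as a daily dose, as both sections state.

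The consequence is limited. If the synopsis line were followed, the habituation exposure and the comparison of GI symptoms after pre-feeding would reflect about one third of the stated dose. The test meal (about 3 cookies, about 10 g of fibre) is unaffected, and the within-subject comparison of glucose IAUC would not by itself be biased. The point should be fixed because it is a threefold conflict in an instruction about the intervention and costs almost nothing to remove.

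**What to change.** Change the synopsis line to 3 cookies with each meal (9 cookies per day), matching Section 4.3. The sponsor can confirm the daily dose of about 29 g when approving the edit.

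Check that the serving size given to subjects under Section 6.2 uses that count, adjusted after the macronutrient analysis. The three-times-a-day wording in the protocol summary and Section 4.1 is correct and needs no change.

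The cost is one line of text and one check of the dispensed serving size, with no extra subjects, visits or procedures.

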2.1 Primary objective

- To compare the 2 hour postprandial glucose incremental area under the curve (IAUC) after the Fibersym containing carbohydrate load with the control meal

2.2 Secondary objectives

- To compare the 2hour postprandial insulin incremental area under the curve (IAUC) after the Fibersym containing carbohydrate load with the control meal
- To compare the individual postprandial glucose and insulin responses at each time point after the Fibersym containing carbohydrate load with the control meal
- To compare the GI symptoms after the three days of pre-feeding of Fibersym cookies with the control meal
- To compare the satiety scores after the Fibersym containing carbohydrate load with the control meal
- SAFETY: GI symptoms and Adverse events.

3. Subject Selection

3.1 Type and number of subjects

Fifteen (15) healthy adult males or non-pregnant females recruited from the pool of subjects who have previously participated in studies at GI Labs and have given permission to be contacted to be recruited for future studies or using online advertising and/or posters. Each subject will have to fulfill all inclusion criteria and will not be allowed to meet any of the exclusion criteria.

3.2 Inclusion Criteria

- Male or non-pregnant females, 18-75 years of age, inclusive
- Body mass index (BMI) between 18.5 and 35 kg/m² inclusive at screening.
- Systolic blood pressure < 130mmHg, Diastolic Blood pressure <90mmHg.
- Willing to maintain habitual diet, physical activity pattern, and body weight throughout the trial.
- Subject is willing to abstain from strenuous exercise, or consume alcoholic drinks 24hours before study days.
- Absence of health conditions that would prevent fulfillment of study requirements as judged by the Investigator on the basis of medical history.
- Understanding the study procedures and willing to provide informed consent to participate in the study and authorization to release relevant protected health information to the study investigator.

- Female subjects are willing to use a contraceptive method to avoid pregnancy during the study period.

3.3 Exclusion Criteria

- Failure to meet any one of the inclusion criteria
- Smokers
- Known history of diabetes, gastrointestinal, liver, kidney, or cardiovascular (including, but not limited to, atherosclerotic disease, history of myocardial infarction, peripheral arterial disease, stroke), and pulmonary disease
- Use of medications known to influence carbohydrate metabolism, including, but not limited to adrenergic blockers, diuretics, thiazolidinediones, metformin and systemic corticosteroids within 4 weeks of the screening visit, or with any condition which might, in the opinion of [name], the president of GI Testing, either: 1) make participation dangerous to the subject or to others, or 2) affect the results.
- Use of antibiotics within 4 weeks of start of study
- Major trauma or surgical event within 3 months of screening.
- Unwillingness or inability to comply with the experimental procedures and to follow GI Labs safety guidelines.
- Known intolerance, sensitivity or allergy to any ingredients in the study products.
- Extreme dietary habits, as judged by the Investigator (i.e. Atkins diet, very high protein diets, etc).
- Change in body weight of >3.5kg within 4 weeks of the screening visit.
- History of cancer in the prior two years, except for non-melanoma skin cancer.
- Exposure to any non-registered drug product within 30 d prior to screening.
- Pregnancy or breastfeeding
- Any history of an eating disorder (e.g., anorexia nervosa, bulimia nervosa, binge eating) diagnosed by a health professional

